6.3 Serious Adverse Event Collection and Expedited Reporting

A serious adverse event is any AE that is:

- fatal, or
- life-threatening, or
- requires or prolongs hospital stay, or
- results in persistent or significant disability or incapacity, or a congenital anomaly or birth defect, or
- an important medical event. Important medical events are those that may not be immediately life threatening, but are clearly of major clinical significance. They may jeopardize the subject, and may require intervention to prevent one of the other serious outcomes noted above. For example, drug overdose or abuse, a seizure that did not result in in-patient hospitalization, or intensive treatment of bronchospasm in an emergency department would typically be considered serious.

Reporting of Serious Adverse Events

SAEs and unanticipated problems posing risks to subjects or others should be reported to the study PI using the SAE case report form (Appendix 2) by the study sites within 24 hours of occurrence.

Investigators are responsible for complying with local IRB reporting requirements. Copies of each report and documentation of IRB notification and receipt will be kept in the investigator's study file. Participating sites will provide the coordinating site with the appropriate documentation of IRB SAE notification and receipt.

The PI will notify the FDA of any unexpected drug-related fatal or life-threatening experience as soon as possible but no later than 7 calendar days from original receipt of the information. All other unexpected drug-related SAEs will be reported no later than 15 calendar days after determination that the event qualifies for reporting.

If a previous AE that was not initially deemed reportable is later found to fit the criteria for reporting, the PI will submit the AE in a written report to the FDA as soon as possible, but no later than 15 calendar days from the time the determination is made.

6.4 *Criteria for Intervention Discontinuation*

A high incidence of medical complications occurs acutely following cervical SCI. As recently reported by Grossman and colleagues, overall complication rates range from 0.15 to 0.30 following SCI in the NACTN registry [20, 21].

- Blood Glucose

Glyburide must be discontinued if the dose has already been reduced in accordance with the defined guidelines and following the reduction (i) there is one lab or repeat point-of-care confirmed BG < 55 mg/dL; OR (ii) there are three lab or repeat point-of-care confirmed BG < 70 mg/dL within a 12-hour period. When glyburide is stopped as a result of BG, D50W or an equivalent amount of dextrose using D5W, D10W, D25W, or D70W (or other concentration) should be administered by bolus in order to maintain BG > 80 mg/dL. Multiple such boluses may be administered, the timing and volume of which are at the discretion of the clinician. BG monitoring is required every 15 (\pm 10) minutes until BG \geq 80 for 3 consecutive readings without bolus glucose supplementation, then hourly (\pm 30 minutes) for the next 6 hours.

- Cardiac

Glyburide must be halted if:

1. A life threatening cardiac-related SAE occurs, whether or not believed by the clinician to be related to glyburide, and/or
 2. Subject experiences QTc of > 550 ms (Bazett's formula) for 15 minutes, whether or not believed by the clinician to be related to glyburide. Before a decision to stop glyburide is made, ECG leads must be repositioned and must be confirmed to be in the correct position, following which the ECG must be repeated in order to confirm QTc > 550 ms.
- Hemolytic Anemia
Glyburide must be discontinued if hemolytic anemia, which in the judgment of the investigator is severe, is detected. In the event of hemolytic anemia, a G6PD deficiency test should be performed following resolution of anemia. This test generally has a multi-day turnaround and will be used for information purposes only.
 - Liver Function
Glyburide must be discontinued if ALT raises to greater than 8-fold the upper limit of normal. Glyburide must be discontinued if the subject develops cholestatic jaundice or hepatitis.

7.0 STATISTICAL CONSIDERATIONS

Descriptive statistics will be generated for all variables of interest. Categorical measures will be reported with frequencies and percentages and continuous measures with means and standard deviations. The frequency of AEs will be reported (as captured on the modified NACTN form) and, where possible, will be compared to those of the matched controls (along with corresponding confidence intervals). We will match study patients and the historical NACTN cohort data on criteria including: age, co-morbidities, injury level, and injury severity (ASIA A, B or C SCI). Additionally, the number of patients who were otherwise eligible for the study but did not enroll due to lack of infusion within 6 hours will be reported. Secondarily, matched tests will be utilized to compare neurologic outcomes between those receiving glyburide and matched historical controls.

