3.0 OBJECTIVES

3.1 Primary Objectives

- **Feasibility:** To assess the feasibility of running a larger phase II or III study among this population of patients where treatment must begin within a defined time frame. The number of patients who would otherwise be eligible for the study but did not receive study treatment within the 8-hour time frame will be recorded (ratio of recruited versus screened). The rate of recruitment will also be recorded.
- **Safety:** Vital signs, clinical exams, ECG, and clinical laboratory results will be carefully and continuously monitored during the course of hospitalization. Adverse events (AEs) will be assessed throughout the course of hospitalization through Day 28. In addition to presenting a summary of all AEs, where possible, a comparison of AEs occurring in study subjects vs. those occurring in matched historical controls (as captured in the NACTN registry) will be made. To facilitate this comparison, AEs will be grouped into one of 10 systems according to a modified NACTN chart [20, 21] (see appendix 1): cardiac, pulmonary, hematology, gastrointestinal/genitourinary, infections, skin, failure of stabilization, neuropsychiatric, hypoglycemia/other metabolic, and other. These AEs will be described further with respect to the specific name of the event (that is, the “type” of event; for example, for cardiac events, the type could be bradycardia or other dysrhythmia, cardiac arrest, etc.). Severity (“intensity”, as per the NACTN chart) as well as relatedness to glyburide will also be assessed. The frequency of AEs, as well as mortality (all-cause and cardiac-related), will be compared to that of a matched cohort from the NACTN registry [20, 21].

Specific outcome variables related to assessing blood glucose (BG)-related safety of glyburide are:

- Hypoglycemia (i.e. Blood Glucose (BG) < 55 mg/dL
- Symptomatic hypoglycemia i.e. hypoglycemia with investigator-identified hypoglycemic symptoms.

The following table defines which BG values should be reported as AEs:

Table 1: Blood Glucose Values and AE reporting

BG Value	Report as AE?
70-79 mg/dL	Mandatory AE reporting not required; may be reported as an AE (and coded appropriately in terms of severity) if the event meets the protocol-defined definitions.
55- 69 mg/dL	Must be reported as an AE, if confirmed by a point-of-care or lab value retest (and coded appropriately in terms of severity)

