< 55 mg/dL	Must be reported as a SAE (appendix 2), if confirmed by either a point-of-care or lab value retest (and coded appropriately in terms of severity)

Specific outcome variables related to assessing cardiac-related safety of glyburide are:

- Incidence/severity of cardiac AEs and cardiac mortality
- Incidence of QTc of > 500 ms
- Mean QTc and mean change in QTc from baseline.

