3. Currently involved in another non-observational SCI research study or receiving another investigational drug
4. History of hypersensitivity to sulfonylureas, in particular glyburide, or any of its components

5. Other illness (including mental disorder) that could preclude accurate medical and neurological evaluation (at discretion of the site investigator)
6. Unable to commit to the follow-up schedule
7. A recent history of regular substance abuse (illicit drugs, alcohol), which in the opinion of the investigator would interfere with the subject's participation in the study
8. Any condition likely to result in the patient's death within the next 12 months
9. Prisoner
10. Severe renal disorder from the patient's history (e.g. dialysis) or baseline eGFR of $< 30 \text{ mL/min/1.73 m}^2$
11. Known severe liver disease, or ALT > 3 times upper limit of normal or bilirubin > 2 times upper limit normal. Subjects may be randomized if liver function tests have been drawn but are not yet available and the subject has no known history of liver disease; however, treatment with glyburide will be discontinued prior to the second dose if liver function tests indicate ALT > 3 times upper limit of normal or bilirubin > 2 times upper limit of normal
12. Blood glucose $< 55 \text{ mg/dL}$ at enrollment or immediately prior to administration of glyburide, or a clinically significant history of hypoglycemia
13. Acute ST elevation myocardial infarction, and/or acute decompensated heart failure, and/or QTc $> 520 \text{ ms}$, and/or known history of cardiac arrest (PEA, VT, VF, asystole), and/or admission for an acute coronary syndrome, myocardial infarction, or coronary intervention (percutaneous coronary intervention or coronary artery surgery) within the past 3 months
14. Known treatment with Bosentan within past 7 days
15. Known G6PD enzyme deficiency
16. Pregnancy: Women must be either post-menopausal, permanently sterilized or, if ≤ 50 years old, must have a negative test for pregnancy obtained before enrollment
17. Breast-feeding women who do not agree to stop breast-feeding during and for 7 days following the end of oral glyburide administration
18. Subjects who in the opinion of the investigator are not suitable for inclusion in the study (reason to be documented).

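### The primary safety objective has no planned patient count of raised ALT or bilirubin, and only one scheduled liver test follows the 96-hour draw

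*Combined protocol and SAP*

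**What the plan says.** Sections 1.2 and 3.1 make safety a primary objective, and section 4.2 plans 10 patients.

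Section 3.1 singles out two safety areas for defined variables: "Specific outcome variables related to assessing blood glucose (BG)-related safety of glyburide are" and "Specific outcome variables related to assessing cardiac-related safety of glyburide are". The cardiac list includes "Incidence of QTc of > 500 ms". There is no liver list.

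The liver limits stand elsewhere:

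- Entry (section 4.1, exclusion 11): ALT above 3x ULN or bilirubin above 2x ULN excludes. The first dose may be given while results are pending, in which case "treatment with glyburide will be discontinued prior to the second dose if liver function tests indicate ALT > 3 times upper limit".
- Stop (section 6.4): "Glyburide must be discontinued if ALT raises to greater than 8-fold the upper limit of normal". Cholestatic jaundice or hepatitis also stops the drug.

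Section 7.0 sets the summaries: "Categorical measures will be reported with frequencies and percentages and continuous measures with means and standard deviations". It also reports adverse event (AE) frequency from the modified NACTN form.

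Liver tests are scheduled at screening, at 24, 48, 72 and 96 h (each ±12 h, section 5.8), and once more by Day 14 or discharge, whichever comes first (section 5.9). The Day 7 draw is for biomarkers; the calendar in 5.11 marks no safety labs that day.

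**The concern.** In a 10-patient safety study, one or two affected patients are the result. A mean and SD do not say how many patients passed a limit, or whether ALT and bilirubin rose in the same patient. The AE count covers part of this, but its criteria contain no ALT multiple, so similar values could be counted at one site and not at another. Section 8.0 rests early termination on review of AEs.

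The stop rule does not close the gap for late values: once dosing is over there is nothing left to stop. The one liver signal the protocol describes (section 2.2) was late. A phase 1 subject had ALT and AST rises that began three days after the drug was stopped.

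**Working it through.** The plan gives no figure to reproduce here. The 10 patients are a feasibility number with no precision calculation.

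**1. Where a liver rise would be counted**

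- As a laboratory variable: mean and SD (7.0). No category is defined.
- As an AE: 6.0 lists five alternative routes, among them symptoms, added treatment or further tests, and investigator judgement. 6.1 describes laboratory abnormalities that need active management. Neither gives an ALT multiple.
- As a stop: only while dosing continues. Twelve doses six hours apart put the last at 11 × 6 = 66 h. The 96 h test (84 to 108 h) and the Day 14/discharge test normally follow it.

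**2. What mean and SD can show** (assumed ALT values in multiples of ULN, n = 10, SD with divisor 9)

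- One at 5.5, nine at 0.7: mean (5.5 + 6.3)/10 = 1.18; SD = √[(4.32² + 9 × 0.48²)/9] = √(20.736/9) = 1.52.
- Two at 4.06, eight at 0.46: mean (8.12 + 3.68)/10 = 1.18; SD = √[(2 × 2.88² + 8 × 0.72²)/9] = √(20.736/9) = 1.52.
- Three at 3.38, seven at 0.237: mean 1.18, SD 1.52.

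The same summary fits 1, 2 or 3 patients between 3x and 8x ULN. At a lower level:

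- One at 3.5, nine at 0.7: mean 0.98; SD = √[(2.52² + 9 × 0.28²)/9] = √(7.056/9) = 0.89.
- Two at 2.66, eight at 0.56: mean 0.98; SD = √[(2 × 1.68² + 8 × 0.42²)/9] = √(7.056/9) = 0.89.

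Here the same summary fits one patient above 3x ULN or none.

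**3. What a count would show** (exact Clopper-Pearson 95% limits; for 0/10 the upper limit is 1 − 0.025^(1/10))

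- 0/10: 0 to 30.8%
- 1/10: 0.25 to 44.5%
- 2/10: 2.5 to 55.6%

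**4. Timing**

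- Latest first-week liver test: 96 + 12 = 108 h.
- Onset three days after the last scheduled dose: 66 + 72 = 138 h. If laboratory hours run from injury and dosing began at 8 h, 146 h. The protocol does not state the time origin.
- Onset after the latest first-week test: 138 − 108 = 30 h to 146 − 108 = 38 h.
- A Day 7 draw at 168 h falls 168 − 146 = 22 h to 168 − 138 = 30 h after onset. If Day 7 is taken as 144 h, the draw lies between 6 h after and 2 h before onset.
- A test on Day 14 (336 h) falls 336 − 146 = 190 h to 336 − 138 = 198 h after onset.
- Longest nominal interval between liver tests: 336 − 96 = 240 h (10 days), an upper end because the last test may come earlier. With a draw at 168 h: 336 − 168 = 168 h (7 days).

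For a patient tested on Day 14, the extra draw therefore matters for rises lasting roughly 1 to 8 days; longer ones are seen either way.

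**The case against.** The strongest reply is that nothing is lost. Every scheduled value is recorded, section 7.0 promises descriptive statistics and does not forbid a threshold table, and with 10 patients the count can be made at analysis. That is true, and it is why the main change is free. What it leaves open is the choice of limits, which should not be made after seeing ten patients' values.

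Other replies also stand:

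- A reader might infer that ALT rises between 3x and 8x ULN would go uncounted, or be AEs only if an investigator chose to call them so. Section 6.0 does not support that: symptoms, treatment or further tests suffice. Appendix 1 is not in the text and may list liver items.
- A reader might infer that ALT above 8x ULN is the only liver stop, or that no liver test beyond the schedule can occur. Jaundice or hepatitis also stops the drug, and 3.1 calls for close laboratory monitoring throughout the hospital stay, so unscheduled tests are possible.
- A reader might take the phase 1 case as a sign that late liver injury is likely here. It was one subject on intravenous 6 mg/day, the size of the rise is not given, and it was normal by Day 22. Dosing here is oral at 2.5 to 3.125 mg/day, and section 2.2 reports nothing new on safety in 93 stroke patients at 3 mg/day.
- The QTc parallel is partial. The counted 500 ms lies below the 550 ms stop, but also below the 520 ms exclusion limit. It shows that the plan counts patients past a limit short of a stop, not that it counts between entry and stop.

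**Conclusion.** The point holds as a recommended, low-cost improvement. The plan has no liver outcome variable for a primary safety objective, and mean and SD cannot supply the patient count: identical summaries fit 1, 2 or 3 of 10 above 3x ULN, or 1 and 0. The ALT values are assumed; that the count cannot be recovered from the summary is arithmetic.

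The schedule point is secondary. It rests on one phase 1 subject and on all doses being given on time. A reader might infer that a late rise would be missed without a Day 7 test; the documents do not show this, since the existing Day 14/discharge test could catch a similar rise. The exception is a patient discharged before about Day 6, whose last scheduled test could precede such an onset. The gain from Day 7 also depends on drawing near 168 h. No gap was shown for blood counts or hemolytic anemia, so the point covers liver tests only.

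**What to change.** **Main change, sections 3.1 and 7.0.** Name liver outcome variables and report the number of patients (x/10, exact 95% CI) whose post-baseline peak is:

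- ALT above 3x ULN
- ALT above 8x ULN
- bilirubin above 2x ULN
- ALT above 3x ULN together with bilirubin above 2x ULN

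Show each against the screening value, because a patient dosed while results were pending may already have been above the entry limit. List affected patients whether or not an AE was recorded, and keep this table apart from the NACTN comparison. The cost is a few lines and one small table from data already collected.

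**Secondary change, sections 5.8 and 5.11.** Add the liver panel to the Day 7 biomarker draw, timed at or near 168 h, and keep the Day 14/discharge test. The cost is one calendar entry and at most 10 panels on blood already being drawn. Some ALT rises will come from trauma, surgery or other drugs, so the listing needs clinical reading, and a Day 7 result may itself lead to an AE.

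The stop thresholds and AE definitions stay as they are.

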3.2 Secondary Objectives

- Pharmacokinetics of glyburide following acute cervical SCI: Plasma concentrations will be serially quantified through day 3 following SCI. Comparisons will be made to reported levels achieved healthy patient cohorts
- Neurologic recovery following SCI: The neurologic status of patients will be assessed using the ASIA Impairment Scale (as assessed by ISNCSCI criteria) and the Spinal Cord Independence Measure (SCIM version III) [22]. The motor and sensory sub scores of the ASIA assessment will be determined on first contact,

every day until Day 4, at 1-2-4-6 weeks, and at 3-6-12 months of follow-up. The SCIM version III will be assessed at 3, 6 and 12 months of follow-up. Comparisons will be made to control subjects (with a 1:3 matching ratio in the NACTN registry matched based on age, co-morbidities, initial injury severity, and injury level.

- Serum biomarker levels: Standard enzyme-linked immunosorbent assay (ELISA) techniques will be used to measure blood levels of neurofilament light chain, neuron-specific enolase, tau, S100b, and glial fibrillary acidic protein levels on admission, at 24 hours and on days 3, and 7 following SCI. Comparisons will be made to (i) matched control serum values of non-treated subjects with acute cervical SCIs [23] and (ii) previously published values observed in non-treated control patients [24-26].
- Spinal cord lesion volumetric analysis: Standard sequences (T1, T2, FLAIR, SWI) at 3T field strength will be used to assess the extent of the hemorrhagic lesion and surrounding edema. Patients will be imaged on the day of admission and on day 2 following injury (standard-of-care studies). Volumetric assessments of lesion size (based on manual outlines) will be performed and compared at the two time-points by the study neuroradiologist to assess for the progression of intrinsic cord signal changes [27].

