4.0 STUDY DESIGN

4.1 Inclusion/Exclusion Criteria

All patients with ASIA A, B or C acute traumatic spinal cord injuries will be assessed for suitability and prospectively enrolled in the study. Only cervical level (C2-C8) level injuries in patients aged 18 to 80 years old will be included. Detailed eligibility criteria are listed below.

The use of immunosuppressive therapy (including methylprednisolone and other corticosteroids) will be discouraged; however, use of such therapy will not require exclusion or discontinuation from the study. While once considered as an option for patients with acute SCI, it is noteworthy that more recent recommendations have all re-

evaluated the routine use of methylprednisolone [28]. The most recent guidelines published by a panel convened by the Joint Section on Spine and Peripheral Nerves of the American Association of Neurological Surgeons and Congress of Neurological Surgeons has in fact recommended against its use following acute SCI given its negative risk- benefit profile [3]. In the words of the panel: “Administration of methylprednisolone for the treatment of acute SCI is not recommended. Clinicians considering methylprednisolone therapy should bear in mind that the drug is not approved by the Food and Drug Administration for this application. There is no Class I or Class II medical evidence supporting the clinical benefit of methylprednisolone in the treatment of acute SCI. Scattered reports of Class III evidence claim inconsistent effects likely related to random chance or selection bias. However, Class I, II, and III evidence exists that high-dose steroids are associated with harmful side effects, including death.” Of note, the recent phase 1/2a riluzole study reported that corticosteroids were administered at the time of admission to only 39% of the patients (while 58% of historic NACTN registry patients had received this treatment) [4].

- **Inclusion Criteria:**

1. Age: ≥ 18 years and ≤ 80 years
2. Written informed consent by patient or legal authorized representative
3. No other life-threatening injury
4. No evidence of sepsis
5. Acute cervical SCI with ASIA Impairment Scale grade A, B or C on admission
6. Non-penetrating SCI at neurologic level from C2 to C8
7. Initiation of study drug within 8 hours of injury

- **Exclusion Criteria**

1. Unconsciousness or other mental impairment that prevents neurological assessment within the first 8 hours
2. Acute SCI with ASIA Impairment Scale grade D or E

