4.4 Study-related management (non-standard of care)

Non-standard-of-care blood work will be obtained at the following time points following the SCI:

- Pharmacokinetic Analysis: Daily, baseline through Day 3
- Biomarkers Levels: Enrollment/Baseline, 24 hours, Day 3, and Day 7

Clinical, imaging, and safety assessments will be performed throughout the study period:

- Patients will be closely monitored clinically for all AEs during the first 28 days of the study. SAEs will be monitored for the entire duration of the study. For the initial hospitalization period, the incidence of AEs will be compared where possible to that of matched controls obtained from the NACTN registry (1:3 ratio with respect to age, co-morbidities, injury level, and injury severity). The 1:3 patient matching will be undertaken by the study statistician.
- Neurological evaluation will be carried out at specific time-points up to one year following SCI to assess for changes in neurological status. The 3, 6, and 12-month ISNCSCI motor/sensory and SCIM vIII scores of the patients will also be compared where possible to that of matched controls from the literature and from the NACTN registry.

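### The 1:3 matching rule does not restrict NACTN controls to patients who meet the trial's own entry criteria, so some controls may be of a kind the trial would not enrol

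*Combined protocol and SAP*

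**What the plan says.** The matching rule is stated in three places. Section 3.2 has controls "matched based on age, co-morbidities, initial injury severity, and injury level". Section 4.4 uses a "1:3 ratio with respect to age, co-morbidities, injury level, and injury severity" and leaves the matching to the study statistician. Section 7.0 will "match study patients and the historical NACTN cohort data on criteria including: age, co-morbidities, injury level, and injury severity", adding that severity means ASIA A, B or C. The wording in 7.0 leaves the list open; the other two sections give it as a plain list of the same four factors.

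The matched cohort serves more than one purpose. Under the primary safety objective in Section 3.1, the frequency of adverse events and mortality "will be compared to that of a matched cohort from the NACTN registry". Neurologic outcomes are compared with the same registry in Section 3.2, and Section 4.4 allows "matched controls from the literature and from the NACTN registry" for them.

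Treated patients face a longer list. Section 4.1 requires "Non-penetrating SCI at neurologic level from C2 to C8", "No other life-threatening injury", no sign of sepsis, and a first dose within 8 hours of injury. Section 4.3 also bars bilateral cervical facet dislocation and fracture patterns with more than 75% canal compromise. Its reason is that the cord damage in such cases probably arises in large part through other mechanisms. No section applies any of this to the registry controls.

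**The concern.** A matched historical comparison is informative only if the controls could have been trial patients apart from the treatment. Matching on four factors makes the groups alike on those factors. It does not remove control patients who differ in injury type or acute status. The protocol itself treats the Section 4.3 fracture patterns as a different kind of injury when it selects patients for treatment, yet the matching rule would accept the same patterns among controls.

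At stake is the comparability of the point estimates for adverse events, mortality and neurologic outcome. The first two belong to a primary objective, and Section 2.0 expects the data to inform phase II/III design. The study is also open-label, so a pool that is not defined in advance could be settled after the treated patients' outcomes are known.

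**Working it through.** There is no design figure to reproduce: the plan gives no power or precision calculation for this comparison. The check has two parts.

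**1. Which entry criteria does the matching already cover?**

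| Criterion for treated patients | Source | Covered by the four factors? |
|---|---|---|
| Age 18–80 | 4.1 | Yes, by age |
| Level C2–C8 | 4.1 | Yes, by injury level |
| ASIA A–C, not D or E | 4.1 | Yes, by severity |
| Renal, hepatic and cardiac history | 4.1 | Partly, by co-morbidity (not defined) |
| Condition likely to be fatal within 12 months (exclusion 8) | 4.1 | Largely, by co-morbidity |
| Not neurologically assessable within 8 hours (exclusion 1) | 4.1 | Largely: without an examination there is no initial grade to match on |
| Non-penetrating injury | 4.1 | No |
| No other life-threatening injury | 4.1 | No |
| No sepsis | 4.1 | No |
| Facet dislocation or canal compromise | 4.3 | No |
| Early enough arrival to be enrolled within 8 hours | 4.1, 5.3 | No |

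The last five rows are the gap.

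**2. How large could the effect be?**

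Inputs: at most 10 treated patients and a 1:3 ratio (Section 1.1), hence 10 × 3 = 30 controls. The registry's pulmonary complication rate of 36.7% and skin complication rate of 16.7% come from Table 4 in Section 6.2.

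- Weight of one control: 1/30 = 3.3 points. Replacing one ineligible control moves a control event rate by at most this much, in either direction.
- Shift if k of 30 controls are ineligible and their event rate differs by d points: ±(k/30) × d. The documents give neither k nor d. Assuming k from 1 to 9 and d from 10 to 30, the range runs from (1/30) × 10 = 0.3 to (9/30) × 30 = 9.0 points, sign unknown.
- Approximate 95% half-width for the difference, treating the groups as independent with a common rate p: 1.96 × √[p(1 − p)(1/10 + 1/30)]. This gives 26.7 points at p = 0.167, 34.5 at p = 0.367 and 35.8 at p = 0.5. The approximation ignores the matching.
- Assumed shift as a share of the half-width at p = 0.367: 0.33/34.5 = 1.0% to 9.0/34.5 = 26.1%.
- Controls whose outcome would have to change, at the full 3.3 points each, to exceed that half-width: 34.5/3.33 = 10.35, so 11 of 30.

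**The case against.** Four arguments can be made on the other side.

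*The plan leaves room.* The list in Section 7.0 is open, and a statistician carries out the matching, who could restrict the pool. True, but nothing requires it, and Sections 3.2 and 4.4 do not leave the list open. The rule is underspecified rather than wrong, and a reader following it could admit the patients described.

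*Matching already does most of the work.* This stands in part. A reader might infer that controls could be patients with "Unconsciousness or other mental impairment that prevents neurological assessment within the first 8 hours", or patients with a short life expectancy. The documents give that little support. Matching on initial grade needs an examination, so only a patient first assessable after 8 hours could slip through. Matching on co-morbidity overlaps heavily with the life-expectancy criterion.

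*The problem may never arise.* The documents do not show whether the registry holds penetrating injuries, or whether it records fracture pattern or arrival time. That limits the claim to what the rule permits. In the same way, a reader might infer from Section 2.1, which says the same network ran a riluzole trial, that treated riluzole patients sit in the control pool. The documents do not show this: on corticosteroid use, Section 4.1 contrasts that trial's patients with historic registry patients as two groups.

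*The effect is small and the study is exploratory.* This also stands. No decision threshold depends on the comparison, the adverse-event comparison is to be made where possible, and Section 10.0 asks for cautious interpretation. It lowers the priority of the point. It does not justify leaving an avoidable systematic difference in place.

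**Conclusion.** The point holds as a minor improvement in comparability. The stated rule can admit controls with penetrating injury, another life-threatening injury, sepsis, the fracture patterns that Section 4.3 bars, or late arrival. No section closes that gap.

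Two stronger conclusions are not supported. One is that the gap makes glyburide look safer or more effective. The documents give neither the registry's mix of such patients nor their outcomes, and Section 4.3 argues from mechanism, not from worse prognosis, so the direction is unknown. The other is that the gap would produce a spurious clear difference. The bound is 3.3 points per control against a half-width of about 34.5 points at a 36.7% rate, and 11 of 30 controls would have to change outcome to exceed it.

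The 0.3 to 9.0 point range rests wholly on the assumed k and d, and the half-widths on an independent-sample approximation with the full 10 and 30 patients. The point is worth acting on because the difference would be systematic, it touches a primary objective, and it can be reduced cheaply before matching.

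**What to change.** Add to Section 7.0:

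> Before 1:3 matching, and without reference to outcomes, the NACTN pool will be restricted to patients who meet the clinically relevant eligibility criteria of Sections 4.1 and 4.3 that the registry records. These include age 18–80, non-penetrating C2–C8 injury, AIS A–C, no other life-threatening injury, no sepsis on admission, and the Section 4.3 CT exclusions. Where the registry records injury-to-admission time, controls who arrived more than 8 hours after injury will be removed. The number of records removed by each criterion, and the criteria that could not be applied, will be reported.

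The cost is one paragraph and a filter in the matching program, with no new data from trial patients. The downside is a smaller pool and possibly looser matches on age or co-morbidity. Thirty controls are 30/485 = 6.2% of the registry patients cited in Section 6.2, but those are not stated to be cervical or ASIA A–C, so the usable pool is unknown. Reporting the removals makes the trade-off visible.

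A separate drafting point: the Section 4.3 CT exclusions are missing from the Section 4.1 list, which presents itself as the detailed criteria. The two sections should be reconciled, since a filter built from 4.1 alone would miss them.
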